9.8.2 Tumor-based Biomarkers

9.8.2.1 Protein Expression

Tumor tissue samples are subject to IHC assays to determine the abundance of TILs and expression of immunoregulatory proteins by the tumor cell, TILs or surrounding stroma cells. Analytes may include, but are not limited to, NKG2A, HLA-E, PD-L1, PD-1, CD3, CD8, and GzmB. Pharmacodynamic changes in TIL prevalence and the presence (and/or abundance) of immunoregulatory and other proteins may be examined. Baseline and pharmacodynamic measures may also be correlated to clinical outcomes.

Tumor tissue may also be used to investigate NKG2A RO and for proteomic analysis or other exploratory analysis of protein expression and characterization.

9.8.2.2 Gene Expression and Mutation Analyses

Sample analyses of mRNA (or micro RNA miRNA) may be completed using RNA isolated from tumor tissue. Targeted or whole transcriptome RNA-sequence, or similar methodologies may be used to assess gene expression signatures, such as, but not limited to, those associated with immune-related signaling, for potential association with clinical outcomes. Focus may be given to monitoring a battery of immunoregulatory genes associated with tumor-infiltrating immune cells. Examples include immunoregulatory genes associated with T cells, NK cells, IFN- γ signaling, and cytolytic activity.

Total DNA will also be isolated from the tumor tissue sample. Whole genome or whole exome sequencing may be performed using this DNA material to investigate potential associations between somatic mutations and copy number variation with efficacy measures. TMB refers to the total number of nonsynonymous somatic mutations that exist within a tumor's genome. High TMB has been hypothesized to correlate with improved efficacy in patients treated with IO therapies. This hypothesis has been supported in multiple publications across IO therapies, tumor types, and lines of treatment.

9.8.3 Blood-based Biomarkers

A variety of biomarkers that may be associated with the treatment efficacy with BMS-986315 will be investigated in peripheral blood specimens taken from all participants prior to and during treatment. Blood samples will be collected prior to and during treatment with BMS-986315 alone or in combination with nivolumab or cetuximab. These blood samples may be assessed for changes in quantity or phenotype of immune cell subsets, changes in soluble factors such as cytokines and chemokines, changes in immune cell functionality, changes in soluble HLA-E, NKG2A RO, changes in NKG2A cell surface expression, changes in gene expression, tumor mutational burden (TMB), or changes in TCR and BCR repertoires. These biomarkers may be used to assess pharmacodynamic changes by dose, and potential associations with efficacy measures, e.g.

objective response. Several sample analyses will be completed and are described briefly below. Additional biomarker assessments may also be performed if samples are available.

9.8.3.1 *Whole Blood for Immunophenotyping*

Flow cytometry will be used to assess baseline and serial on-treatment alterations in composition/activation status of immune-cell subsets present in the whole blood samples obtained from all participants in each treatment arm. Lymphocyte subsets to be assayed may include, but not be limited to, CD8+ and CD4+ T-cell subsets, NK cells and populations of those cells as defined by the expression of activation, exhaustion, or signaling markers, such as Ki67, human-leukocyte antigen-antigen D-related, cytolytic markers, and/or PD-1. Monocytes/macrophages and dendritic cell populations may also be monitored in a similar fashion, with a focus on characterizing subsets defined by the expression of lineage-specific markers.

9.8.3.2 *Serum Factors*

To understand the level of soluble circulating proteins and the impact they may have on the clinical activity of the study treatments, the protein concentrations of a panel of cytokines, chemokines, and other relevant immunomodulatory, soluble factors may be investigated by enzyme-linked immunosorbent assay (ELISA) or other relevant immunoassay methods. Examples of specific analytes to be assessed may include, but are not limited to, factors induced by IFN- γ signaling (eg, T-cell chemoattractants CXCL9 and CXCL10), cytolytic markers (eg, granzyme A/B, perforin), SARS-CoV-2 serologic status, and soluble HLA-E.

9.8.3.3 *Whole Blood DNA*

Whole blood collected from participants prior to study treatment initiation may be used to generate genomic DNA for the understanding of genetic variation analyses. These analyses will focus on genetic variations within genes associated with or affecting immunoregulatory signaling to explore if natural variation within those genes is associated with a response to each component of the combination treatment.

Additionally, genomic DNA from whole blood may be used as a comparator for participants with tumors examined by whole-exome or genome-mutation analysis. Whole-exome or whole-genome sequencing methods may be used for this analysis. Lastly, genomic DNA from whole blood may be used for TCR sequencing.

9.8.3.4 *Plasma for Circulating Tumor DNA*

Plasma samples may be collected at the time points indicated in Table 9.8-1. Plasma ctDNA may be assessed for association with tumor mutational burden (TMB).

9.8.3.5 *Peripheral Blood Mononuclear Cells*

Whole-blood samples may be collected for isolation and cryopreservation of PBMCs. These cryopreserved samples may be used for functional activation tests, for additional assays if new biology suggests analysis beyond the immunophenotyping described above, and for TCR sequencing if needed.

9.8.3.6 Additional Research Collection

This protocol will include residual sample storage for additional research (AR).

For All US sites:

Additional research is required for all study participants, except where prohibited by IRBs/ethics committees, or academic/institutional requirements. Where one or more of these exceptions occurs, participation in the additional research should be encouraged but will not be a condition of overall study participation.

- If the IRB/ethics committees and site agree to the mandatory additional research retention and/or collection, then the study participant must agree to the mandatory additional research as a requirement for inclusion in the study.
- If optional participation is permitted and approved, then the study participants may opt out of the additional research retention and/or collection.

For non-US Sites

Additional research is optional for all study participants, except where retention and/or collection is prohibited by local laws or regulations, ethics committees, or institutional requirements.

This collection for additional research is intended to expand the translational R&D capability at Bristol Myers Squibb, and will support as yet undefined research aims that will advance our understanding of disease and options for treatment. It may also be used to support health authority requests for analysis, and advancement of pharmacodiagnostic development to better target drugs to the right patients. This may also include genetic/genomic exploration aimed at exploring disease pathways, progression and response to treatment etc.

Sample Collection and Storage

All requests for access to samples or data for additional research will be vetted through a diverse committee of the study sponsor's senior leaders in Research and Development (or designee) to ensure the research supports appropriate and well-defined scientific research activities.

Residual samples from PK, IMG, biomarker, and tumor biopsy collections (see [Table 9.8.3.6-1](#)) will also be retained for additional research purposes.

Samples kept for future research will be stored at the BMS Biorepository [REDACTED] or an independent, BMS-approved storage vendor.

The manager of these samples will ensure they are properly used throughout their usable life and will destroy the samples at the end of the scheduled storage period, no longer than fifteen (15) years after the end of the study or the maximum allowed by applicable law.

Transfers of samples by research sponsor to third parties will be subject to the recipient's agreement to establish similar storage procedures.

Samples will be stored in a coded fashion, and no researcher will have access to the key. The key is securely held by the Investigator at the clinical site, so there is no direct ability for a researcher to connect a sample to a specific individual.

Further details of sample collection and processing will be provided to the site in the procedure manual.

Table 9.8.3.6-1: Residual Sample Retention for Additional Research Schedule

Sample Type	Timepoints for which residual samples will be retained
PK	All
Tumor Biopsy	All
Blood Biomarker Samples	All

9.9 Health Economics OR Medical Resource Utilization and Health Economics

Health Economics/Medical Resource Utilization and Health Economics parameters will not be evaluated in this study.

10 STATISTICAL CONSIDERATIONS

10.1 Sample Size Determination

The approximate total number of participants treated will be up to 308 for Part 1 as shown below:

- In Part 1A, approximately 36 participants will be treated in dose escalation phase, and up to 40 participants will be treated in SCCHN PD cohort, for a total of up to approximately $36+40=76$ participants.
- In Part 1B, with 2 SCCHN PD cohorts, up to approximately $36+40+40=116$ participants will be treated, with 36 participants in dose escalation phase, and 40 participants in each SCCHN PD cohort.
- In Part 1C, similar to part 1B, up to approximately $36+40+40=116$ participants will be treated.

10.1.2 Part 1 PD Cohorts

Sizing of PD cohort in each of Parts 1A, 1B, and 1C is based on getting a reasonable estimate of the PD signal difference between biomarker negative and positive population. The PD signal of primary interest to be assessed is tumor cytolytic activity. Assuming natural prevalence of biomarker positive (~70%) in SCCHN population, we expect to enroll biomarker positive participants to biomarker negative participants in the ratio of 2:1. With a total sample size of 30 participants (20 biomarker positive and 10 biomarker negative), the two-sided 80% confidence interval for the difference in the pharmacodynamic signal between the biomarker positive and biomarker negative is (14%, 46%). This assumes a 5% probability of tumor cytolytic activity in the biomarker negative and 35% probability of cytolytic activity in the biomarker positive subgroups, respectively.

In order to account for 25% non-evaluable biopsy samples or lack of repeat biopsy due to early dropouts, about 10 more participants would be needed. That is in order to have 30 evaluable participants, up to approximately 40 will need to be treated per dose level of the SCCHN PD cohorts in monotherapy and combination therapy.

10.2 Populations for Analyses

For purposes of analysis, the following populations are defined in Table 10.2-1 below:

Table 10.2-1: Populations for Analysis	
Population	Description
All Enrolled	All participants who signed an ICF and were registered into the IRT.
All Treated	All enrolled participants who receive at least 1 dose of study drug.

Table 10.2-1: Populations for Analysis

Population	Description
Response-evaluable	All treated participants with measurable disease at baseline and 1 of the following: (a) at least 1 post baseline tumor assessment, (b) radiologic progression, (c) death.
PK	All treated participants that have available serum concentration data that allow for computation of PK parameter values.
Immunogenicity	All Treated participants with baseline and at least 1 pre-infusion immunogenicity assessment.
Biomarker	All Treated participants who have available biomarker data.

Abbreviations: ICF = informed consent form; IRT = Interactive Response Technology; PK = pharmacokinetics.

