Procedure ^a	Cycle 1 (28 days)				Cycle 2 (28 days)				Cycle 3 and Beyond (28 days)				EOT ^b	Notes
	D1	D8 ^c	D15 ^c	D22 ^c	D1 ^c	D8 ^c	D15 ^c	D22 ^c	D1 ^c	D8 ^c	D15 ^c	D22 ^c		
Biomarker Assessments														
Tumor Biopsy ^e	See Section 9.8 and Table 9.8-1												On treatment biopsy should be performed on C1D22 (plus or minus 5 days)	
Blood, Serum, and Plasma Pharmacodynamic Sampling, and SARS-CoV-2 Serology	See Section 9.8 and Table 9.8-1												SARS-CoV-2 serum will be collected predose at C1D1 and collected approximately every 6 months during study treatment to be used for potential future measurements of anti-SARS-CoV-2 serology (anti-SARS-CoV-2 total or IgG). SARS-CoV-2 serum should also be collected approximately 4 weeks after a documented or suspected anti-SARS-CoV-2 infection.	
Imaging Assessments^f														
Body Imaging	See Notes												Contrast enhanced CT of the chest, CT/MRI of the neck (required for SCCHN participants), abdomen, pelvis, and all other known and/or suspected sites of disease will occur every 8 weeks starting 8 weeks from date of first dose (\pm 7 days) until disease progression and treatment discontinuation, whichever occurs	

Table 2-2: On Treatment Procedural Outline (CA047004)

Procedure ^a	Cycle 1 (28 days)				Cycle 2 (28 days)				Cycle 3 and Beyond (28 days)				EOT ^b	Notes
	D1	D8 ^c	D15 ^c	D22 ^c	D1 ^c	D8 ^c	D15 ^c	D22 ^c	D1 ^c	D8 ^c	D15 ^c	D22 ^c		
														later. See Section 9.1.1.1 for further details.
Brain Imaging														Participants with a history of brain metastasis or symptoms should have a surveillance MRI study per standard of care (approximately every 12 weeks), or sooner if clinically indicated. CT of the brain without and with contrast can be performed if MRI is contraindicated. See Section 9.1.1.1 for further details
Study Treatment														
BMS-986315 Administration (Part 1A, 1B and Part 1C)	X				X				X					If a dose is delayed, the procedures scheduled for that same timepoint should also be delayed to coincide with when that timepoint's dosing actually occurs.
Nivolumab Administration (Part 1B only)	X				X				X					
Cetuximab Administration (Part 1C only)	X		X		X		X		X		X			

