8 DISCONTINUATION CRITERIA

8.1 Discontinuation from Study Treatment

Participants MUST discontinue investigational product (and non-investigational product at the discretion of the investigator) permanently for any of the following reasons:

- Participant's request to stop study treatment. Participants who request to discontinue study treatment will remain in the study and must continue to be followed for protocol specified follow-up procedures. The only exception to this is when a participant specifically withdraws consent for any further contact with him/her or persons previously authorized by participant to provide this information
- Any clinical AE, laboratory abnormality or intercurrent illness which, in the opinion of the investigator, indicates that continued participation in the study is not in the best interest of the participant
- Documented disease progression as defined by RECIST v1.1 ([Appendix 7](#)) unless participants meet criteria for treatment beyond progression ([Section 5.1.5](#)).

- Clinical deterioration while receiving active study therapy that, in the opinion of the Investigator, indicates that continued participation in the study is not in the best interest of the participant.
- Any drug-related AE occurring at any time that meets DLT criteria as outlined in [Section 5.1.3](#) will require permanent discontinuation.
- Inability to comply with protocol.
- Discretion of the investigator.
- Pregnancy.
- Termination of the study by Bristol Myers Squibb (BMS)
- Loss of ability to freely provide consent through imprisonment or involuntarily incarceration for treatment of either a psychiatric or physical (eg, infectious disease) illness. (Note: Under specific circumstances and only in countries where local regulations permit, a participant who has been imprisoned may be permitted to continue as a participant. Strict conditions apply and BMS approval is required.)
- Individual participants with confirmed CR will be given the option to discontinue study therapy on a case by case basis after specific consultation and agreement between the investigator and BMS Medical Monitor in settings where benefit/risk justifies discontinuation of study therapy.
- Any event that leads to delay in dosing lasting > 8 weeks from the previous dose requires discontinuation, with the following exceptions:
 - Dosing delays to allow for prolonged steroid tapers to manage drug-related adverse events are allowed.

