10.3.1 Efficacy Analyses

The main efficacy analyses (Table 10.3.1-1) will be performed on the treated population, presented separately by study part. Efficacy analyses based on the response-evaluable population may be performed for interim analyses when the minimum follow-up period is less than sufficient to warrant adequate interpretation of the result.

Table 10.3.1-1: Efficacy Statistical Analysis

Endpoint	Statistical Analysis Methods
ORR is defined as the proportion of population of interest whose BOR is either CR or PR per RECIST v1.1 BOR for a population of participants will be assessed per RECIST v1.1.	Estimate of ORR and corresponding 2-sided exact 95% CI using the Clopper-Pearson method by treatment for each tumor type
Median DOR DOR for a participant with a BOR of CR or PR is defined as the time between the date of first response and the date of the first objectively documented tumor progression per RECIST v1.1 or death, whichever occurs first.	Median duration of response using the Kaplan-Meier method and corresponding 2-sided 95% CI using Brookmeyer and Crowley methodology (using log-log transformation) by treatment for each tumor type Analysis is dependent on the number of responders
PFSR at 6, 9, and 12 months PFS for a participant is defined as the time from the first dosing date to the date of first objectively documented disease progression or death due to any cause, whichever occurs first.	Estimate by the Kaplan-Meier method and corresponding 95% CI will be derived based on Greenwood formula by treatment for each tumor type.

Abbreviations: BOR, best overall response; CI, confidence interval; CR, complete response; DOR, duration of response; ORR, overall response rate; PFS, progression free survival; PFSR, progression free survival rate; PR partial response; RECIST, Response Evaluation Criteria In Solid Tumors

Overall survival rate (OSR) at 1 year and 2 years will be analyzed similarly to PFSR. Details of the censoring scheme on time-to-event endpoints such as DOR, PFS, and OSR will be described in the Statistical Analysis Plan.

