10.3.8 Interim Analysis

Interim analyses will be performed prior to the end of the study, e.g. at the completion of a study part such as the end of the escalation phase (in 1A, 1B or 1C), or at the completion of a PD cohort, for evaluation of the available data in that study part. No formal inferences requiring any adjustment to statistical significance level will be performed.

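### The optional interim response-evaluable set leaves out clinical progression, so clinical failures who are alive and never scanned drop out of the ORR denominator

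*Combined protocol and SAP*

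**What the plan says.** Section 10.2, Table 10.2-1, admits to the response-evaluable set treated participants with measurable disease at baseline who also have one of "a) at least 1 post baseline tumor assessment, (b) radiologic progression, (c) death".

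Section 10.3.1 sets out how the set is used. The main efficacy analyses "will be performed on the treated population, presented separately by study part". For short follow-up there is an alternative: "Efficacy analyses based on the response-evaluable population may be performed for interim analyses". In the same section, "ORR is defined as the proportion of population of interest whose BOR is either CR or PR per RECIST v1.1", with a "corresponding 2-sided exact 95% CI using the Clopper-Pearson method by treatment for each tumor type". Section 10.3.8 places interim analyses at points such as the end of an escalation phase or of a PD cohort, and states: "No formal inferences requiring any adjustment to statistical significance level will be performed".

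Three other places decide who can be left out:
- Section 8.1 lists, separately from RECIST progression, "Clinical deterioration while receiving active study therapy that, in the opinion of the Investigator", makes continued participation contrary to the participant's interest.
- Table 2-2 (Section 2) schedules body imaging "every 8 weeks starting 8 weeks from date of first dose", with a 7-day window either side, until the later of progression and treatment discontinuation. Section 9.1.1.2 likewise has tumor assessments go on after dosing stops.
- Table 2-3 and Section 5.1.4.2 schedule follow-up scans only for participants with SD, PR or CR.

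**The concern.** An interim response-evaluable set has a sound purpose: to set aside participants whose first scan is not yet due. As written, it also sets aside some whose outcome is already known to be poor. A participant who deteriorates clinically in the first 8 weeks and stops has failed treatment. If nobody scans that participant and no death is recorded by the cut-off, none of the three criteria applies.

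The exclusion depends on outcome, and it removes only non-responders. Section 10.1.1 lets preliminary efficacy, if available, contribute to the recommended Phase 2 dose, and ORR is reported by treatment and tumor type, where counts can be very small. With four participants and one responder, losing one unscanned failure turns 1/4 (25%) into 1/3 (33%). If early clinical stops differ between doses, the distortion differs between them too.

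**Working it through.** **Plan's own figures.** The plan states no expected share of unscanned clinical failures and no target ORR, so there is no figure of this kind to reproduce. The denominator used below is the 40 treated per PD cohort (Section 10.1.2), which does reproduce: 30/(1 - 0.25) = 40. That 25% allowance concerns biopsies, not RECIST evaluability, so it is not evidence about f.

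**Illustrative response rates.** Section 3.3 gives 27.5% for another NKG2A antibody with cetuximab; 11/40 = 27.5%. Section 3.2.3 gives about 13% for cetuximab; 5/40 = 12.5% is close.

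**Formula.** Let n be the set that counts clinical failures, x the responders, and k the clinical failures who are alive and never scanned, with f = k/n.
- ORR counting them: x/n.
- ORR as written: x/(n - k) = (x/n) × 1/(1 - f).
- With x = 0 both are zero. With x ≥ 1 and k ≥ 1 the second is larger.

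**Mature cut-off, n = 40** (f is an assumption; exact 95% CI in brackets):

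| k | f | 11 responders | 5 responders |
|---|---|---|---|
| 0 | 0% | 11/40 = 27.5% (14.6-43.9) | 5/40 = 12.5% (4.2-26.8) |
| 2 | 5% | 11/38 = 28.9% (15.4-45.9) | 5/38 = 13.2% (4.4-28.1) |
| 4 | 10% | 11/36 = 30.6% (16.3-48.1) | 5/36 = 13.9% (4.7-29.5) |
| 8 | 20% | 11/32 = 34.4% (18.6-53.2) | 5/32 = 15.6% (5.3-32.8) |

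The relative increases are 1/0.95 = 1.05, 1/0.90 = 1.11 and 1/0.80 = 1.25.

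**Immature cut-offs.** Simulation of 200,000 participants, all inputs assumed: true ORR 27.5%; 10% with clinical progression before Week 8 and no scan; 5% dying before Week 8; uniform accrual over 12 months; response seen at Week 8 and confirmed at Week 16. In the last column of each block, clinical progressors enter when they progress.

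Clinical progressors alive at the cut-off:

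| Cut-off after last enrolment | All treated | As written | Counting clinical progression |
|---|---|---|---|
| 0 weeks | 19.1% | 25.0% | 22.3% |
| 8 weeks | 23.4% | 25.9% | 23.4% |
| 16 weeks | 27.5% | 30.5% | 27.5% |

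Clinical progressors dying a mean of 17 weeks after progression:

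| Cut-off after last enrolment | All treated | As written | Counting clinical progression |
|---|---|---|---|
| 0 weeks | 19.0% | 22.9% | 22.1% |
| 8 weeks | 23.4% | 24.0% | 23.4% |
| 16 weeks | 27.5% | 27.9% | 27.5% |

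The excess of the set as written over the set that counts clinical progression is 2.7, 2.5 and 3.0 points in the first case and 0.8, 0.6 and 0.4 points in the second. In the second case it shrinks over time because the death criterion brings these participants back in. At 0 and 8 weeks the estimate as written is still below the true 27.5%, because responders awaiting confirmation sit in the denominator only.

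**The case against.** The best defence is that the set has limited use. The main ORR counts every treated participant, the response-evaluable analysis is optional and interim, and no formal inference follows. TITE-BOIN itself uses only DLT and safety information. Section 10.3 also leaves the selection of participants to a later SAP. All of this stands, and it limits the consequence to an optimistic descriptive estimate at an interim look.

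Four stronger readings are tempting, and the documents do not support them.
- **That radiologic progression adds nobody beyond the first criterion.** The two overlap heavily, but Section 9.1.1 lets X-rays and bone scans show progression, and Appendix 7 (Section 2.2.2) lets a new lesion on chest X-ray, or certain FDG-PET findings, count as PD. Someone with such a finding before any CT/MRI assessment can enter through this criterion alone.
- **That all early clinical failures, or all who stop early for toxicity, are lost.** Those who die stay in. Under Table 2-2 and Section 9.1.1.2, those who stop without documented progression are still due scans and enter once scanned. The leak is the participant who is not scanned. Table 2-3 and Section 5.1.4.2 leave room for that, because a participant with no post-baseline scan has no SD, PR or CR status.
- **That interim ORR must exceed the true rate.** The increase is relative to a set that counts these failures. Confirmation lag can leave the estimate below the truth, and with no responders nothing changes.
- **That the size is known.** No document supports any value of f, and only alive, never-scanned participants belong in it.

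**Conclusion.** The point holds in a limited form. Table 10.2-1 omits clinical progression, and treated participants with measurable disease who stop for clinical deterioration before Week 8, are not scanned later and are alive at the cut-off leave the interim denominator. With at least one responder, this raises interim ORR by 1/(1 - f) against a set that counts them. At an assumed f of 5-10% the shift is 1.4 to 3.1 points on 11/40 (28.9 - 27.5 and 30.6 - 27.5), well inside the exact 95% CI of 14.6-43.9%. It is smaller if these participants die before the cut-off. The all-treated ORR is unaffected. The direction follows from the definition; the size rests on the assumed f. The change is worth making because the exclusion depends on outcome and serves no purpose of the set.

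**What to change.** Keep the three existing criteria and add a fourth to Table 10.2-1: clinical progression, or discontinuation of study treatment, with no post-baseline tumor assessment by the time the first scan was due. Count these participants as non-responders unless a later scan documents a confirmed response.

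Two details of the wording matter. Radiologic progression should not be replaced, because that could drop participants whose progression was seen only on X-ray, bone scan or FDG-PET. Nor should every stop before the first scan be a non-response outright: Appendix 7 runs best overall response to progression rather than to the end of dosing, so someone who stops early can still have a confirmed response later.

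Show the all-treated ORR beside any response-evaluable ORR. The rule can go in the SAP that Section 10.3 foresees, provided that it is settled before the first interim efficacy analysis. The cost is one added phrase, one added column in the interim tables, and a slightly less favourable interim ORR.
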